scd14	Soluble CD14
SIV	Simian immunodeficiency virus
TGF- β	Transforming growth factor beta
TUNEL	Terminal deoxynucleotidyl transferase dUTP nick end labeling
TNF	Tumor necrosis factor
TZ	T-cell zone
Treg	Regulatory T cell
UMMC	University of Minnesota Medical Center
VL	Viral load

Protocol Summary

Full Title	Reversing Tissue Fibrosis to Improve Immune Reconstitution in HIV
Conducted By	National Institute of Allergy and Infectious Diseases (NIAID)
Principal Investigator	[name] Professor of Medicine University of Minnesota, Department of Medicine
Sample Size	50 HIV infected subjects and 10 HIV uninfected control subjects.
Study Population	HIV infected : Inclusion: Healthy, HIV-1 positive men and women ≥ 18 years of age, with CD4 count 200-650 cells/ μ l, on stable antiretroviral therapy (ART). Exclusion: Pregnancy, use of drugs that suppress or enhance immune function, current use of angiotensin converting enzyme inhibitor (ACEi) or angiotensin-2 receptor blocker (ARB). HIV uninfected : Inclusion: Healthy, ≥ 18 years of age. Exclusion: Pregnancy, use of drugs that suppress or enhance immune function, current use ACEi or ARB.
Accrual Period	14 months
Study Design	This is a single-center, double-blinded, placebo-controlled study of HIV infected, ART treated subjects randomized 1:1 to daily losartan or placebo for 30 months. All HIV infected subjects will undergo biopsies of inguinal lymph node (LN) and gut associated lymphatic tissue (GALT) at baseline, 12 and 30 months after study enrollment. Blood will be collected at least quarterly throughout the study and an intensive blood pharmacokinetic (PK) study will be conducted at month 1. All HIV infected subjects will be vaccinated with the quadrivalent human papillomavirus (HPV) vaccine at months 23, 25 and 29.5. HIV uninfected control subjects will not receive study agents or HPV vaccination and will undergo blood draw and inguinal LN biopsy at one time point only.
Sub-study-MRI	10 HIV+ subjects will be randomly selected to participate in the MRI sub-study and the 5 control subjects will be enrolled in the MRI sub-study. We are collecting preliminary data to determine if there is potential for a MRI to monitor levels of collagen in lymph nodes. We will image the node that will be removed in the losartan parent trial to have collagen levels measured. We think it possible that this non-invasive procedure might someday be used as a biomarker in studies of anti-fibrotic therapy in HIV infection.
Study Duration	HIV infected subjects will be followed for 30 months. HIV uninfected subjects will have up to four study visits. We expect to complete follow up of all subjects 44 months after the first subject is enrolled.
Study Agent/Intervention Description	Losartan 100 mg daily (starting at 50 mg and dose escalating to tolerance) vs. Placebo For the five additional controls: Stribild – 150 mg elvitegravir/150 mg cobicistat/200 mg emtricitabine/300 mg tenofovir disoproxil fumarate once daily and Prezista – 800 mg once daily

Primary Endpoint	Impact of losartan on lymphoid tissue (LT) fibrosis as determined by the amount of collagen deposition in LT and integrity of the fibroblastic reticular cell network (FRCn).
Secondary Endpoints	
 1. Impact of losartan on immune reconstitution and T cell function. 2. Impact of losartan on immune activation. 3. Impact of losartan on HIV viral reservoir size. 4. Determination of potential drug-drug interactions between losartan and ART.
Exploratory Endpoints	
 1. Assess the impact of losartan on frequency of dendritic cell and CD4 T-cell interactions with the FRCn using two-photon microscopy. Given that this is an exploratory endpoint, we will perform these assays in a subset of subjects (5 losartan treated, 2 placebo treated, and 10 HIV uninfected controls). 2. To develop methods to image collagen content of inguinal lymph nodes using MRI 3. To measure drug levels and pharmacokinetic (PK) profile of antiretrovirals in lymph tissues of HIV uninfected people.

2. BACKGROUND INFORMATION AND SCIENTIFIC RATIONALE

2.1 Background Information

The goal of combination antiviral therapy (cART) in HIV is to suppress viral replication and restore immune function. It is possible with modern cART to suppress plasma viremia to below detectable limits in most people; however immune reconstitution (IR) is often incomplete, and significant immunologic abnormalities persist, even after years of therapy. CD4 T cell populations in peripheral blood mononuclear cells (PBMC), lymph node (LN), and gut associated lymphoid tissue (GALT) do not reconstitute to normal levels [1-4], responses to vaccines remain abnormal [5-8], and life expectancy continues to be significantly decreased compared to age-matched controls [9]. The underlying mechanisms driving these persistent immune abnormalities are likely related to the fact that markers of immune activation (IA) do not normalize in treated patients [10-12]. Indeed, there is growing evidence to support a model of persistent IA during therapy driving disease progression, albeit at a much slower rate than in untreated patients.

Causes of persistent IA before and during therapy include ongoing virus production [13], co-infections such as cytomegalovirus (CMV) [14], and microbial translocation (MT) of bacterial products across a persistently damaged gut epithelium [12, 15, 16]. IA inevitably leads to pathologic changes in lymphoid tissues (LT) that significantly alter their function and limit immune reconstitution (IR). The primary pathology of persistent IA in LT is collagen deposition in the parafollicular T-cell zone (TZ) of secondary LN and GALT that gradually destroys TZ structure [17, 18]. Collagen deposition is mediated by transforming growth factor beta (TGF- β) that is made by regulatory T cells (Treg) recruited into LT in an attempt to control virus production [19-21]. During chronic and treated infection, when virus production is either substantially or completely suppressed, co-infections and MT may play a larger role in TGF- β production. Irrespective of the cause, TZ collagen accumulates over time and leads to depletion of naive and central memory (CM) CD4 T cells and prevents IR when cART is begun [17, 22]. Collagen destroys the fibroblastic reticular cell network (FRCn) which is a mesh of hollow fibers that form the skeletal anatomy of the TZ [23]. T cells require contact with the FRCn in order to migrate through the TZ and initiate immune responses and gain access to IL7 (made by the FRCn) required for survival [24-26]. Collagen formation in the TZ is a cause of naive and CM depletion and prevents their full reconstitution when cART is begun. Thus TZ collagen plays a critical role in HIV pathogenesis, and therapies to eliminate its presence may be an important adjunctive therapy to improve IR.

We have used the TGF- β inhibitor pirfenidone in a non-human primate model of LT fibrosis induced by SIV infection. Pirfenidone is a drug licensed outside of the U.S. for the treatment of idiopathic pulmonary fibrosis (IPF) and it blocks TGF- β at the level of phosphorylation of SMAD 2,3 in the TGF- β signaling pathway [27-34]. We show that animals receiving pirfenidone plus cART had significantly less TZ collagen, a more normal FRCn and significantly greater numbers of CD4 T cells in PBMC and LN. Pirfenidone is not FDA approved and the manufacturer is unable to make it available for this study. However, an alternative drug exists that may be superior to pirfenidone. Losartan is an FDA-approved angiotensin receptor inhibitor (ARB) that inhibits TGF- β at the level of phosphorylation of SMAD 2,3 [35-38] with animal and human studies to show it reverses existing fibrosis in lung, liver, and kidney [39-43]. It is widely used throughout the world in Marfan syndrome for its antifibrotic properties. Importantly, distinct from pirfenidone, losartan also decreases inhibitors of matrix metalloproteases that prevent tissue remodeling and increases proteases that induce tissue remodeling [39, 44, 45]. Further, it has anti-inflammatory properties that may be uniquely beneficial in the context of HIV infection. It inhibits LPS-induced inflammatory signaling, an important component of MT, and decreases levels of tumor necrosis factor (TNF), IL6, and soluble adhesion molecules [46, 47].

2.2 Study Hypothesis and Rationale

Our hypothesis is that treatment of HIV infected subjects with losartan, which has specific anti-inflammatory and anti-fibrotic actions will: 1) reverse existing fibrosis, 2) restore LN architecture, 3) increase the number and improve the function of peripheral and lymphatic CD4 T cells, 4) decrease levels of IA, 5) decrease HIV reservoirs, and 5) be safe and well tolerated. To address this hypothesis, we will enroll HIV infected subjects and randomize them 1:1 to losartan vs placebo, then serially sample blood and LT. In similar longitudinal tissue biopsy protocols our drop-out rate has ranged from 20-25%. Therefore, we plan to enroll 63 HIV infected subjects in order to have 50 complete the protocol. All HIV infected subjects randomized to losartan will initiate therapy at a dose of 50 mg per os (po) daily and increase the dose to 100 mg po daily if they have no side effects or laboratory abnormalities after 14 days. This is standard losartan dosing for the treatment of hypertension and stroke reduction. This dosing protocol was also used and was well tolerated by non-hypertensive subjects in a large clinical trial assessing the anti-fibrotic effect of losartan in patients with Marfan syndrome [48]. Given risk of teratogenicity with losartan, all female subjects of reproductive age who are enrolled in the protocol will be required to use a reliable and effective method of contraception for the duration of the study. Lymphatic tissue biopsies for primary endpoint analysis will be obtained at baseline and 12 and 30 months after initiation of losartan or placebo. We are following subjects for 30 months because we felt that a long period of follow up may be required to discern a significant difference in the treatment groups given the persistence of LT fibrosis in subjects treated with ART alone (unpublished data). HIV infected subjects will also be administered the human papillomavirus (HPV) quadrivalent vaccine (Gardasil) per the manufacturer's recommended dosing schedule to assess immune response (a secondary endpoint). Gardasil vaccine is FDA-approved for use in men and women ages 9 to 26 to prevent the complications related to infection with HPV types 6, 11, 16 and 18. Although not approved for adults >26 years of age, the vaccine has been well-studied in older populations and has been found to be safe and well-tolerated [49-51]. It is expected that many study subjects will have been exposed to 1 or more of the HPV serotypes included in the vaccine; however, based on epidemiologic data, it is not expected that subjects will have been exposed to all 4 serotypes [52-54]. Therefore, this vaccine can be used to assess both neo and recall immune responses. Vaccination will be initiated at the end of the study to maximize time on study drug prior to vaccination and to ensure that tissues are collected at time of maximal immune response.

Though there are no known or anticipated drug interactions between losartan and ARVs, this has not been extensively studied. Therefore an intensive pharmacokinetics experiment will be conducted on all HIV infected subjects at month 1 of the study (when losartan is at steady state). In addition, levels of ARVs and losartan in plasma and PBMCs will be performed quarterly over the 30-month study period and intracellular levels of losartan and ARVs will be measured in LT at month 30. These analyses will be performed in semi real-time to ensure that subjects are not put at risk from unexpected drug-drug interactions.

We will enroll 5 HIV uninfected subjects who will not be randomized to a treatment arm and will not be given HPV vaccination. They will undergo a blood draw and inguinal LN biopsy at one time point only. We will enroll an additional 5 HIV uninfected subject who will not be randomized to a treatment arm nor given HPV vaccine. These 5 subjects will be given Stribild and Prezista for two weeks. In previous studies with HIV-positive individuals, we have shown lymph node concentrations of all ARVs to be suboptimal. No one has yet measured ARV concentrations in lymph nodes of healthy volunteers; we feel this is an excellent opportunity to answer that question. These subjects will return to the medical center for an inguinal LN biopsy and colonoscopy and blood draws at baseline, hours 1, 2, 3, 4, 6, 8, 12 and 24 at one time point only. The five control subjects who are taking Stribild and Prezista will be part of the MRI-sub-study (See Appendix I). This test will occur once during the two weeks while they are taking the antiretrovirals, prior to the biopsy.

In addition, these negative controls are important to the success of the two-photon microscopy experiment, which is used to measure motility of lymphocytes on the LN FRCn. The HIV negative control group will be

used to determine normal motility and samples obtained from HIV infected subjects on losartan and placebo will then be compared to these results. We have preliminary data from similar experiments conducted in mice to suggest that 10 control subjects will be adequate to establish normal motility.

2.3 MRI Sub-study

This sub-study will involve 10 regular subjects & the 5 new HIV-negative controls.

Subjects will be randomly selected to participate in the MRI sub-study. We are collecting preliminary data to determine if there is potential for a MRI to monitor levels of collagen in lymph nodes. We will image the node that will be removed in the losartan parent trial to have collagen levels measured. We think it possible that this non-invasive procedure might someday be used as a biomarker in studies of anti-fibrotic therapy in HIV infection. (See Appendix I for the MRI sub-study protocol).

2.4 Potential Risks and Benefits

2.4.1 Potential Risks

Potential risks of study procedures (venipuncture, inguinal LN biopsy, and colonoscopy with GALT biopsies) are detailed in Section 7.1 and in consent forms. According to the Losartan package insert, the most severe risks of losartan use include teratogenicity in the setting of pregnancy, hypersensitivity, symptomatic hypotension, worsening of renal function, and electrolyte abnormalities. The most common side effects of losartan include fatigue, weakness, diarrhea, chest pain, tachycardia and anemia.

Subjects will be rigorously screened to ensure that they are at low risk for complications due to losartan and they will be monitored closely for side effects and signs of toxicity. The most common side effects of Gardasil include headache, fever, nausea, dizziness and injection site reactions. Severe reactions, including hypersensitivity, are rare. The most common side effects of Stribild are new onset or worsening of renal impairment, bone effects, fat distribution and immune reconstitution syndrome. The most common side effects of Stribild include nausea, diarrhea, abnormal dreams, headache, rash, fatigue, dizziness, insomnia, flatulence, somnolence, ocular icterus and jaundice. The most common side effects of Prezista are drug –induced hepatitis, skin reactions ranging from mild to severe, use with caution with a known sulfonamide allergy, new onset diabetes or hyperglycemia, redistribution/accumulation of body fat or immune reconstitution syndrome and subjects with hemophilia may develop increased bleeding events, The most common side effects of Prezista include diarrhea, nausea, rash, headache, abdominal pain and vomiting.

2.4.2 Potential Benefits

All subjects (excluding control subjects) will receive results of clinical laboratory testing and HPV vaccination at no cost over the course of this study. There are no other direct benefits of participation for the individual subjects. However, the proposed research has the potential to significantly benefit people infected with HIV.

3. STUDY OBJECTIVES

3.1 Primary Objective

We will assess the impact of losartan on LT fibrosis in HIV infected, ART treated adults by measuring the amount of collagen deposition in LT and the integrity of the FRCn using IHC.

3.2 Secondary Objectives

To determine the impact of losartan on immune reconstitution and T- cell function, immune activation, HIV viral reservoir size, and to determine any potential drug-drug interactions between losartan and ART.

3.3 Exploratory Objectives

1. Assess the impact of losartan on frequency of dendritic cell and CD4 T-cell interactions with the FRCN using two-photon microscopy.
2. To develop methods to image collagen content of inguinal lymph nodes using MRI
3. To measure drug levels and pharmacokinetic (PK) profile of antiretrovirals in lymph tissues of HIV uninfected people.

4. STUDY DESIGN

4.1 Description of the Study Design:

This is a randomized, double-blind, placebo-controlled trial of 50 HIV-1 infected individuals on stable ART randomized in a 1:1 ratio to losartan (50 mg orally daily titrated to 100 mg daily) vs placebo for 30 months. We plan to enroll a total of 63 HIV infected subjects to ensure that 50 complete the protocol. All HIV infected subjects will undergo biopsies of inguinal lymph node (LN) and gut associated lymphatic tissue (GALT) for primary endpoint analysis at baseline, 12 and 30 months after study enrollment. Blood will be collected at least quarterly throughout the study and an intensive blood pharmacokinetic (PK) study will be conducted at month 1. All HIV infected subjects will be vaccinated with the quadrivalent human papillomavirus (HPV) vaccine at months 23, 25 and 29.5. 5 HIV uninfected control subjects will also be enrolled. They will not receive study agents or HPV vaccination and will undergo blood draw and inguinal LN biopsy at one time point only. We anticipate completing subject enrollment over a 14 month period and plan to complete all subject follow up 44 months after the first subject is enrolled.

4.2 Study Endpoints:

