5. STUDY POPULATION

5.1 Selection of Study Population

83% of persons living with HIV/AIDS in the State of Minnesota are male, 50% are white, 32% black (with 10% being African born), 9% Hispanic/Latino, 4% American Indian, and 5% Asian or “Other” (Minnesota Department of Health 2010 data). By focusing on women and minority populations in our recruitment efforts, we anticipate that the demographic profile of our study participants will represent this distribution.

HIV infected subjects will be recruited using our well-established recruitment network in the Twin Cities that involves partnerships with local HIV clinics and community organizations such as the Minnesota AIDS Project. We will also design study specific advertisements and flyers for use in local publications and clinics. HIV uninfected subjects will be recruited through flyers placed around the University of Minnesota and advertisements in local magazines and newspapers.

As above, based on drop-out rates in similar studies we have conducted in the past, we plan to enroll a total of 63 HIV infected subjects to ensure that 50 complete the protocol.

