8. STUDY SCHEDULE

8.1 Schedule for HIV infected subjects (n=50)

8.1.1 Screening

At this visit, consents will be reviewed in detail and the subject will have the opportunity to ask any questions they may have. Subjects will be asked if they would like to participate in the additional two-

photon microscopy sub-study which entails additional blood draws at several scheduled study visits. Designated study staff or physician will interview the participant and a physical exam (which includes vital signs and exam of heart, lungs, abdomen, neurologic and lymphatic systems) will be performed. Blood will be obtained for CD4 T cell count, HIV VL, HIV antibody, liver function tests, electrolyte panel including creatinine, and complete hematology count (CBC - white blood cell count with differential, hemoglobin and platelets). Screening for hepatitis C will also be performed. Women of childbearing age will have a urine pregnancy test. Once lab results are available (within 3 days), they will be reviewed by designated study staff to ensure that laboratory inclusion/exclusion criteria are met. If the subject has met all entry criteria, they will be contacted by the designated study staff. The study protocol will again be reviewed and if they are still interested in enrolling, they will be scheduled for the day 0 visit. Subjects who have not met the criteria will also be contacted by the designated study staff and told that they do not qualify to participate in the study. At this visit, an "enroll by date" will be designated that is no more than 60 days from the screen date to ensure screening labs are no more than 60 days old at the time of randomization. If more than 60 days passes between "Screen" and randomization, a comprehensive chemistry panel will be redrawn with the results known to be within study-required parameters prior to randomization.

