9.7.2 Stopping Rules for an Individual Participant

Subjects may withdraw from the study (and all follow-up procedures) for any reason and at any time. Participants may also choose to discontinue study medication and continue all follow-up procedures. This is most likely in the event of a toxicity that, in the opinion of the investigators, is related to the study agents.

If a subject withdraws, attempts will be made to schedule and conduct an early termination visit as described in section 8.1.11. The reason and date of withdrawal will be documented on the subject's CRF. Date of withdrawal will be documented as the date of last study drug treatment, not the date that the decision to withdraw was made. Participants will be followed after withdrawal from the study for 3 months after discontinuation. All AEs during that period will be reported.

The PIs may withdraw participants to protect their safety or if participants are unable or unwilling to comply with visits, study procedures, or study medication. Participants will be removed from the study if they experience any drug-associated toxicity > grade 2 and it is judged to be due to losartan (e.g., a complication of the biopsy procedure may not necessitate removal from the study). Subjects will not be withdrawn if they experience toxicity > grade 2 that is deemed due to Gardasil but will not continue to be given Gardasil. Subjects will also be removed in the event of pregnancy. Healthy controls will be removed from the study if they experience rash, moderate GI symptoms and/or symptoms consistent with clinical hepatitis with no other medically reasonable cause. Other exit criteria include:

- completion of the study,
- withdrawal of consent,
- moving to an area that would prohibit the subject from returning for visits, and
- death.

Even though subjects may be withdrawn prematurely from the study, we will continue to collect survival data on such subjects throughout duration of the 30 months. If a subject withdraws consent to participate in the study, attempts will be made to obtain permission to record survival data up to the 30-month end point. Methods used for follow up will include at least 5 phone calls and 3 letters to the participant.

Any subject withdrawn from the study prior to Month 1 will be replaced by another enrolled participant to meet study objectives.

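### Enrolling 63 gives an expected 50 completers only if dropout is at most 20.6%, while the protocol's own dropout range is 20% to 25%

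*Combined protocol and SAP*

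**What the plan says.** Section 2.2 gives the dropout experience: "In similar longitudinal tissue biopsy protocols our drop-out rate has ranged from 20-25" per cent. It then draws the enrolment figure from that range: "we plan to enroll 63 HIV infected subjects in order to have 50 complete the protocol". Sections 4.1 and 5.1 repeat the figure in stronger terms. Section 4.1 has "We plan to enroll a total of 63 HIV infected subjects to ensure that 50 complete the protocol", and section 5.1 has "we plan to enroll a total of 63 HIV infected subjects to ensure that 50 complete the protocol".

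Section 9.7.2 adds a replacement rule: "Any subject withdrawn from the study prior to Month 1 will be replaced by another enrolled participant to meet study objectives". It provides no replacement for later losses.

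Section 11.2 gives power for a two-sample t-test with 25 subjects per group and a standard deviation of 0.81 on the log scale. For differences of 0.5, 0.6, 0.7 and 0.8 the stated power is 0.59, 0.75, 0.86 and 0.94. Neither alpha nor sidedness is given there, and section 11.5 refers only to conventional levels.

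**The concern.** An enrolment figure derived from a dropout range should hold across the range, or the text should say which end it uses. Here the range is 20% to 25%, yet the single figure of 63 is offered as enough to secure 50 completers. If it reaches 50 only at the favourable end, the promise in sections 4.1 and 5.1 is stronger than the protocol's own inputs allow. The power table in section 11.2 would then describe a number of completers that the stated enrolment may well not deliver.

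**Working it through.** **Inputs.** Enrolment 63 and target 50 completers (2.2, 4.1, 5.1); dropout 20% to 25% (2.2); SD 0.81, 25 per group and the four differences (11.2). The mid-range value of 22.5% is added here. Two-sided alpha of 0.05 is an assumption.

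**1. Reproduce the plan's figure.** Required enrolment is N = 50/(1 − d). At d = 0.20, 50/0.80 = 62.5, which rounds up to 63. The plan's figure is therefore correct for 20% dropout. At d = 0.25, 50/0.75 = 66.7, which rounds up to 67.

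**2. Break-even dropout.** 63 − 50 = 13, and 13/63 = 20.6%.

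**3. Expected completers, and the chance of at least 50.** Expected completers are 63 × (1 − d). The chance is the binomial probability of 50 or more out of 63 with completion probability 1 − d, assuming independent dropout and no replacement.

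| Dropout | Expected completers | Chance of at least 50 |
|---|---|---|
| 20% | 63 × 0.80 = 50.4 | 0.62 |
| 22.5% | 63 × 0.775 = 48.8 | 0.43 |
| 25% | 63 × 0.75 = 47.25 | 0.26 |

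The expected counts do not need the independence assumption; the chances do. Enrolling 67 would not guarantee 50 either: at 25% dropout the same calculation gives 0.59.

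**4. What replacement could do.** Suppose replacements are additional to the 63, and let f be the share of all dropouts that occur before Month 1. Expected completers are then 63(1 − d)/(1 − f·d). Setting this equal to 50:

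- At d = 0.25: 1 − f·d = 47.25/50 = 0.945, so f = 0.055/0.25 = 0.22.
- At d = 0.225: 1 − f·d = 48.825/50 = 0.9765, so f = 0.0235/0.225 = 0.10.

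Replacement would restore an expected 50 if at least 22% of dropouts (at 25% dropout) or 10% (at 22.5%) came before Month 1. The documents give no timing for past dropouts. If replacements come from within the 63, the table in step 3 stands as it is.

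**5. Effect on power.** The normal approximation is Φ(δ/(σ√(2/n)) − 1.96). With σ = 0.81 and n = 25 the standard error is 0.81 × √0.08 = 0.229. The exact t values use the noncentral t distribution. The last row takes 47 completers split 24 and 23.

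| Difference | 0.5 | 0.6 | 0.7 | 0.8 |
|---|---|---|---|---|
| Stated in 11.2 | 0.59 | 0.75 | 0.86 | 0.94 |
| Normal approximation, 25 + 25 | 0.588 | 0.745 | 0.863 | 0.937 |
| Exact t, 25 + 25 | 0.571 | 0.728 | 0.849 | 0.928 |
| Exact t, 24 + 23 | 0.544 | 0.700 | 0.826 | 0.912 |

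The normal approximation reproduces the plan's table in all four cells. Like for like (exact t in both rows), losing three completers costs 2.7, 2.8, 2.3 and 1.6 points.

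**The case against.** The strongest reply is that 63 contains no arithmetic error: it is right at 20%, which lies inside the protocol's range. That stands. A reader might notice that 50 × 1.25 = 62.5 also rounds up to 63 and infer that the wrong inflation formula was used. Since 50/0.80 gives the same result, the documents do not support that inference. What remains is that an optimistic end of the range was used without saying so, and that the result is described as ensured.

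Second, other provisions soften the effect. Section 9.7.2 replaces early withdrawals and lets participants stop study drug while staying in follow-up. The mixed model in section 11.1 can use month 12 biopsies from people who leave later, so no analysis depends on having exactly 50 completers. This stands too, and it is why the point is minor. It does not show that the gap closes, because neither the counting of replacements nor the timing of past dropouts is stated.

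Three stronger readings are tempting and should not be adopted:

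- A reader might infer that the power table in section 11.2 is wrong because exact t values are 1 to 2 points lower. The table is an ordinary planning approximation, it sets no target power, and the planned test is a Wald test from a mixed model.
- A reader might see a contradiction in the sample size, because the synopsis has "50 HIV infected subjects and 10 HIV uninfected control subjects" and section 4.1 opens with a "trial of 50 HIV-1 infected individuals on stable ART randomized in a 1:1 ratio to losartan". The next sentence of section 4.1, like sections 2.2 and 5.1, explains 63 as enrolment and 50 as completers. What is left is editorial.
- A reader might infer that the DSMB would misjudge losses to follow-up. Section 10.1.1 lists that task but does not tie it to 50 completers.

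**Conclusion.** The point holds and is minor. Enrolling 63 gives an expected 50 completers only up to 20.6% dropout, so across most of the protocol's own 20% to 25% range the expected number falls short, by up to about three. Even at 20% the chance of reaching 50 is about 62%, so the claim to ensure it is not supported anywhere in the range. The expected counts rest only on the protocol's figures, before any replacement. The chances also assume independent dropout and no replacement. The power loss of roughly 2 to 3 points assumes two-sided 0.05, an even split of losses and a completer-only t-test. It does not show that the trial is underpowered or that more subjects are needed, since the plan sets no target power and its model also uses the month 12 data.

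**What to change.** Enrolment, conduct and analysis stay as they are.

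1. In sections 2.2, 4.1 and 5.1, replace the statements that 63 will yield or ensure 50 completers with wording such as: *about 47 to 50 completers are expected at 25% to 20% dropout, before any replacement of withdrawals before Month 1*.
2. In the same places, or in section 9.7.2, state whether replacements are additional to the 63.
3. In section 11.2, note that the table is a normal approximation for 25 + 25 completers, and state the alpha and sidedness used. If these are two-sided 0.05, give the exact t values of 0.57, 0.73, 0.85 and 0.93. Add that with about 47 completers exact t power is about 0.54, 0.70, 0.83 and 0.91, and that this is a completer approximation to the planned mixed model.

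The cost is a text edit and a slightly less favourable stated completer number and power.
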